#### 5.1.4. Missing Values for GOS-E

GOS-E at [REDACTED] 180 will be analyzed as a 7-category ordinal scale (1/2, 3, 4, 5, 6, 7, 8). Multiple imputation will be used to account for missing values for GOS-E. Death and vegetative state are scored as 1 and 2 in GOS-E and therefore no missing GOS-E values are expected due to death or vegetative state. Missing GOS-E values due to reasons other than death or vegetative state will be imputed based on a linear model performed on the GOS-E scores leveraging the information of the patient at other time points as well as the time patterns of all other participants. The model will include treatment as a classification variable and other covariates: GOS-E score at the previous timepoint, region (North America and RoW), age ( $\leq 70$ ,  $> 70$  years), baseline GCS (5-8, 9-12, 13-15), baseline contusion volume per investigator ( $> 3$  to 10 mL vs  $> 10$  mL). Imputed values will be rounded to the closest valid GOS-E score, 100 imputations will be conducted with random seed pre-specified, and each imputation will result in a complete dataset for all mITT participants.

The missing data pattern will be evaluated including reasons for missingness, missing data by randomized treatment group and visit, and potential covariates associated with missingness. Sensitivity analyses will be planned to evaluate the robustness of the results from the main analysis of GOS-E.

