### 5.6.1. General Analysis Methods for Efficacy Endpoints

All endpoint models (binary logistic regression, ordinal logistic regression, Cox model, and analysis of covariance) below will regress the outcome on the randomized treatment group, comparing the BIIB093 combined with placebo groups, adjusting for all the IRT stratification factors at randomization (see [Section 3.5.1](#)), baseline contusion volume per the central review and baseline GCS.

Analysis of covariance (ANCOVA) will be performed to compare the change in total contusion volume (primary analysis), change in absolute hematoma volume, the change in absolute edema volume, [REDACTED] from baseline in the main analysis comparing the BIIB093 combined with placebo groups. The least square (LS) mean difference with the corresponding 2-sided 95% CI and p-values for the treatment group will be provided.

Binary logistic regression will be used for binary outcomes comparing the BIIB093 combined with placebo groups. Odds ratio, the corresponding 2-sided 95% confidence interval (CI) and p-value will be reported for the treatment group.

Ordinal logistic regression (proportional odds model) will be used for GOS-E as a 7-category ordinal scale (1/2, 3, 4, 5, 6, 7, 8) and for mRS as a 5-category ordinal scale (0/1, 2, 3, 4, 5/6) at Day 90 and 180. Odds ratio, the corresponding 2-sided 95% CI and p-value for the treatment group will be reported.

The proportional odds ratio assumption will be tested using likelihood ratio test based on observed data. In the case the assumption does not hold (p-value < 0.05) or non-convergence, the Mann-Whitney test will be used as the primary inference and the source of non-proportionality or non-convergence will be investigated. Following the Mann-Whitney test, dichotomized analysis will be conducted to assess the treatment effects.

The Cox proportional hazard model will be used to assess the treatment effect on overall survival at Day 90 for all randomized participants. Hazard ratio, 2-sided 95% CI as well as the p-value for the treatment group will be reported. Kaplan-Meier curves will be presented by randomized treatment group, and Greenwood's formula will be used to calculate the standard error of the Kaplan-Meier estimates.

Multiplicity will be not be adjusted for the tests of the primary and secondary endpoints, since the current study sample size is not powered for a moderate treatment effect on GOS-E.

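### SAP 5.1.4 sets no floor when it imputes Day 180 GOS-E, so participants known to be alive and not vegetative can be imputed into the worst category (1/2)

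*SAP*

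**What the plan says.** Day 180 GOS-E is analysed in seven ordered categories, with scores 1 and 2 merged. SAP 5.1.4 starts from the fact that "Death and vegetative state are scored as 1 and 2 in GOS-E" and concludes that "no missing GOS-E values are expected due to death or vegetative state". It continues: "Missing GOS-E values due to reasons other than death or vegetative state will be imputed based on a linear model performed on the GOS-E scores". The model draws on the participant's other time points "as well as the time patterns of all other participants". Then: "Imputed values will be rounded to the closest valid GOS-E score", and "100 imputations will be conducted with random seed pre-specified".

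The imputation model contains treatment, the previous GOS-E score and the four stratification factors: region, age band, GCS band and investigator-assessed contusion volume band. The analysis model in SAP 5.6.1 also has centrally read baseline contusion volume and a baseline GCS term alongside the GCS stratum.

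Protocol 16.2.2.3 calls for multiple imputation of Day 180 GOS-E without further detail. SAP Table 3 names ordinal logistic regression with multiple imputation as the main analysis. SAP 5.6.3 combines the imputed results by Rubin's rule and also lists an ordinal analysis of observed data. SAP 5.1.4 promises sensitivity analyses for GOS-E but specifies none.

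**The concern.** The section reasons that deaths and vegetative states are already scored, so the values to be imputed belong to people missing for other reasons. It then uses a rule that can hand those people a score of 1 or 2. The model is also fitted with deaths in the data, which pulls predictions for survivors downward.

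Because 1 and 2 form one analysis category, the error counts when someone who belongs at 3 or above is placed in the bottom category, or when imputed scores sit too low overall. Both distort the category distribution of the secondary endpoint listed first in the plan. The amendment summary for protocol version 3 says that Day 180 was preferred because it is the registrational endpoint in TBI studies.

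**Working it through.** **1. The plan's own figure.** The plan gives no figure for GOS-E imputation. Its only power statement is for the primary endpoint (SAP 2.3: 80 v 80, difference 15 mL, SD 29 mL). The standardised difference is 15 / (29 × √(2/80)) = 3.27, and Φ(3.27 − 1.96) = 90.5% (90.2% by noncentral t). It reproduces and has no bearing on this point.

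**2. Can the rule return 1 or 2?** SAP 5.1.4 names 1 and 2 as GOS-E scores, so both are valid targets for rounding. It sets no lower bound, does not exclude scores 1 and 2 from the fit, and has no step for vital status. Protocol 16.2.2.3 and SAP 5.6.3 add no bound. So yes.

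**3. Chance per draw.** For a normal draw with mean μ and residual SD σ, P(rounded score is 1 or 2) = Φ((2.5 − μ)/σ). The residual SD is an assumption.

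| Predicted score | σ = 0.8 | σ = 1.0 | σ = 1.2 | σ = 1.5 |
|---|---|---|---|---|
| 3 | 26.6% | 30.9% | 33.8% | 36.9% |
| 4 | 3.0% | 6.7% | 10.6% | 15.9% |
| 5 | 0.1% | 0.6% | 1.9% | 4.8% |
| 6 | 0.0% | 0.0% | 0.2% | 1.0% |

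For example, at μ = 4 and σ = 1.5, Φ(−1.5/1.5) = Φ(−1) = 15.9%. The problem sits with participants whose earlier scores are low.

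**4. Share over all imputed values.** This was simulated with 150 or 160 participants, a linear fit to everyone, proper parameter draws and rounding to 1-8. All score distributions, death rates and missing rates are assumptions, and fewer than the planned 100 imputations were used where the number was recorded (5 or 20).
- With 15% missing, Day 90 mortality 5-20%, deaths between Day 90 and Day 180 of 0-5%, and SD of change 0.7-1.0, 3-10% of imputed values were 1 or 2. Among those scoring 3 at Day 90 the share was 11-31%. Nobody imputed was truly 1 or 2. The covariates other than treatment and previous score were left out.
- Other assumed settings gave 1.0-5.0%, 1.7-7.7%, 3-6% and 6.4-9.5%. The mean imputed score was too low by 0.05-0.24, 0.08-0.39, 0.2-0.4 and 0.4-0.5 points respectively.

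Together this is about 1-10% of imputed values and 0.05-0.5 points. At 15% missing, at most 0.15 × 160 = 24 people are imputed, so 0.24 to 2.4 per imputed dataset land in 1/2.

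**5. Mechanism.** Deaths scored 1 at both visits lower the predictions. They do not materially widen the residual SD. With deaths against survivors only, it was 0.70 v 0.73, 0.89 v 0.93 and 1.07 v 1.10 when the mean gain from Day 90 to Day 180 was zero. It was about equal at a gain of 0.4 and at most 0.04 higher at a gain of 0.8. Deaths between the two visits do raise the share imputed as 1/2. With 5% Day 90 mortality and SD of change 0.7, raising late deaths from 0 to 5% moved it from 3.1% to 8.6%.

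**6. Effect on the odds ratio.**
- Equal missingness: the log odds ratio was 0.569 under the SAP rule v 0.568 with full data. In another setting (15% missing) it was 0.356 v 0.353, with SE 0.299 v 0.290.
- Unequal missingness, one assumed setting: 0.538 under the SAP rule v 0.577 with full data. That is (0.577 − 0.538)/0.577 = 7% attenuation on the log scale, or an odds ratio of 1.71 instead of 1.78. Predictive mean matching within 3-8 restored 0.577.

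**7. Are both parts of the remedy needed?** Fitting only to participants scored 3-8 cut the mean shift to 0.03-0.09 points, but 1-3% of draws still fell below 3. The restricted fit and the bounded values are both needed. With both, the share in 1/2 is zero by construction.

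**The case against.** The strongest reply concerns what the SAP actually asserts. A reader might infer that everyone imputed is, on the SAP's own statement, alive and not vegetative, so that every imputed 1 or 2 is an error. The documents do not support that. SAP 5.1.4 speaks of the reason for missingness, not of verified status. Follow-up stops when consent is withdrawn (Protocol 7.2, 10.3), and someone is lost to follow-up only after contact attempts and other sources, which may include death records, have failed (Protocol 10.2). Vital status can then be unknown, and some probability of category 1/2 is right. This part stands: a 3-8 bound for everyone would replace one wrong assumption with a more optimistic one.

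A reader might also infer that the rule biases the treatment effect in general. It does not: step 6 shows almost no movement under equal missingness. The bias under unequal missingness is modest and shown in one assumed setting. A third tempting inference, that deaths scored 1 at both visits inflate the residual SD, fails at step 5.

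The covariate gap is small. All four stratification factors, including GCS in bands, are in the imputation model. Only central-read volume and the second GCS term are absent, and no effect of omitting them has been shown.

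Mitigation is partial. The plan reviews reasons and patterns of missingness and lists an observed-data analysis. Table 3 nonetheless names multiple imputation as the main method, and the sensitivity analyses are unspecified, so no stated check would reveal the problem.

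Finally, this is a secondary endpoint in a Phase 2 trial without multiplicity control, and SAP 5.6.1 says the sample is not powered for a moderate GOS-E effect. That limits the weight of the point but does not remove it.

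**Conclusion.** The point holds for participants known to be alive and not vegetative at Day 180. As written, the rule can place them in category 1/2, and it shifts imputed survivors downward. The ranges in step 4 are conditional, because the documents state none of the inputs that determine them, and the practical impact grows with the amount of missing data. The main exposure is a biased category distribution. Bias in the odds ratio needs missingness that differs between arms, and the one case examined was modest. The change is worth making because the better method is standard and cheap, not because the trial's conclusions are shown to be at risk.

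**What to change.** Amend SAP 5.1.4 as follows.

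1. **Known deaths** stay at 1, and observed scores of 2 stay at 2.
2. **Known alive and not vegetative at Day 180, score missing:** impute with an ordinal logistic or predictive-mean-matching model fitted to participants scored 3-8, with allowed values 3-8. Include treatment, earlier GOS-E scores and every covariate of the analysis model, including central-read baseline contusion volume. Say what evidence counts as known alive and not vegetative.
3. **Vital status unknown:** use a separate stated step that allows category 1/2, for example imputing vital status first, or an ordinal model over all categories.
4. Keep the 100 imputations, the pre-specified seed and Rubin's rule as planned.

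The cost is SAP wording, a different imputation option in the software and slightly more programming for the vital-status split. No new data are needed, and the primary endpoint and its power are untouched.

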#### 5.1.5. Missing Values for mRS

The mRS [REDACTED] at Day 180 will be analyzed as a 5-category ordinal scale (0/1, 2, 3, 4, 5/6). No multiple imputation will be used to account for missing values for mRS.

## 5.2. Participant Accountability

The summaries in the end of treatment status section will be based on all randomized participants. Participant end-of-treatment status will be summarized in total and by randomized treatment group. The summary statistics include:

- Number (%) of participants randomized and dosed.
- Number (%) of participants who complete the treatment.
- Number (%) of participants who discontinue the treatment, and reason(s) for not completing the treatment will be summarized.

A participant listing of reasons for treatment discontinuation will be provided for all enrolled participants.

The summaries in the end of study status section will be based on the follow-up set. Participants end-of-study status will be summarized in total and by randomized treatment group. The summary statistics include:

- Number (%) of participants who enter 90-day (180-day) follow-up and have at least one assessment after the Day 90 visit.
- Number (%) of participants who complete the study.
- Number (%) of participants who withdraw from the study, and reason(s) for not completing the study.

A participant listing of reasons for study withdrawal will be provided for all enrolled participants.

## 5.3. Demographic and Baseline Characteristics

Demographic and baseline characteristics will be summarized by randomized treatment group for mITT and all randomized participants, respectively, unless specified otherwise. For continuous or numerical variables, the summary statistics will include number (%) of participants with non-missing measurements, mean, standard deviation (SD), median, quartiles (Q1, Q3), and range (min, max). For categorical (nominal or ordinal) variables, summary statistics include number (%) of participants in corresponding analysis population and number (%) of participants in each level of the categorical variable. The number (%) of participants with missing measurements will be provided for both continuous and categorical variables, if applicable.

### 5.3.1. Demographics per CRFs

- Age (years) at screening
- Age category at screening ( $\leq 60$ , 60 to 70,  $> 70$  years)
- Sex (female, male, other)
- Race (White, African-American, Asian, Other)

- Ethnicity (Hispanic, Non-Hispanic)
- Geographic region (North America, RoW)

### **5.3.2. Baseline Disease Characteristics per CRFs**

- Time (hours) to randomization post injury or LKN
- Time (hours) to initiation of study drug infusion post injury or LKN
- Time (hours) to NCCT for eligibility post injury or LKN
- Time (hours) to initiation of study drug infusion from NCCT for eligibility
- Injury types
- Baseline GCS before randomization
- Total injury severity scoring (ISS) score excluding head or face
- Baseline brain contusion volume (mL) per investigator
- Baseline brain contusion volume (mL) per the central review
- Baseline hematoma volume (mL) per the central review
- Baseline edema volume (mL) per the central review
- Baseline blood glucose
- Baseline alcohol level
- Baseline sodium

### **5.3.3. Stratification Factors per IRT**

- Baseline contusion volume per investigator
  - > 3 to 10 mL
  - > 10 mL
- Baseline Glasgow Coma Scale (GCS)
  - 5 to 8
  - 9 to 12
  - 13 to 15
- Baseline age
  - $\leq$  70 years old
  - > 70 years old
- Region
  - North America (United States and Canada)
  - Rest of World (RoW)
- Concordance rate of stratification factors per IRT and per CRFs by strata and overall

### **5.3.4. Physical Measurements at Baseline**

The physical measurements will be captured for the participants during hospitalization.

- Height (cm)
- Weight (kg)
- Body mass index (BMI; kg/m^2)

### 5.3.5. Medical History

Medical history (medical condition or surgical procedure) will be coded using the Medical Dictionary for Regulatory Activities (MedDRA), if applicable.

- The number (%) of participants with medical history (including ongoing and stopped conditions) will be summarized.
- A participant listing of medical history will be provided.

### 5.4. Protocol Deviations

Protocol deviations identified during site monitoring will be captured in the Protocol Deviation Log and categorized as major or minor deviations.

- Number (%) of participants with any major protocol deviations will be summarized by randomized treatment group for mITT participants.
- A listing of major and minor protocol deviations for all randomized participants will be provided.

### 5.5. Study Treatment Exposure and Concomitant Medications

#### 5.5.1. Study Treatment Exposure

The extent of study treatment exposure will be summarized by actual treatment group for the safety analysis set in the Day 4 database. The total amount (mg) of study drug received via infusion is calculated from the infusion rate with start and stop date/time and volume administered (bolus and re-bolus only). The duration of study drug administration (hours) is calculated from the first bolus date/time to the last infusion date/time. The duration of study drug infusion (hours) is calculated from start/stop date/time of each bolus or infusion (the duration of study drug administration minus the dose interruption intervals).

- Total amount of study drug will be summarized by treatment group.
- Duration of study drug administration will be summarized by treatment group.
- Duration of study drug infusion will be summarized by treatment group.
- Number (%) of participants with any infusion interruptions and reason for the first interruption for a participant will be summarized by treatment group.
- Number (%) of participants with any rate changes and reason for the first change for a participant will be summarized by treatment group.
- Listing of reasons for interruption, rate change and dose reduction will be provided.
- Listing of kit numbers will be provided.

#### 5.5.2. Concomitant Medications

All concomitant medications will be coded using the World Health Organization (WHO) medication dictionary.

- Number (%) of participants taking any concomitant medications will be summarized by randomized treatment group and total and by indication for mITT participants.
- A listing of concomitant medications for randomized participants will be presented.

### 5.5.3. Non-drug Therapies

A concomitant therapy (including medication or non-drug therapy) is defined as any therapy that is taken on or after the start date/time of study drug infusion. This includes therapies that are started prior to start of study drug infusion if their use continues after study drug infusion. If a participant never receives study drug, date of randomization will be used, if applicable. Handling of partial or missing start/stop date/time is described in [Section 5.1](#). Concomitant non-drug therapies will be coded using MedDRA.

The following non-drug therapies will be summarized by randomized treatment group and total and by indication for mITT participants:

- Number (%) of participants taking any non-drug therapies.
- Number (%) of participants requiring NSx including craniotomy and DC, time and the reasons of DC.
- Number (%) of participants with decision of CMO, time and reasons of CMO.
- Number (%) of participants requiring delayed intubation, time and reasons of delayed intubation.

A listing of non-drug therapies for randomized participants will be provided.

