### 3.6.1. Full Analysis Set

The full analysis set, i.e., the modified intention-to-treat (mITT) participants, will include all the participants who are randomized, receive any study drug (BIIB093 3 mg/day, BIIB093 5 mg/day or the matching placebo), and have at least one final read per central review of contusion volume from an NCCT or MRI scan acquired between 10 hours after the initiation of study drug infusion and the Hour 96 visit or NSx or CMO (if earlier). In efficacy analyses performed on the full analysis set (mITT participants), participants will be analyzed according to the randomized treatment group (see [Section 3.2.1](#) for the definition).

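### Counts of NSx/DC, CMO and major protocol deviations are tabulated only in mITT, a set whose definition leaves out some of the participants those tables are meant to count

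*SAP*

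**What the plan says.** SAP 5.5.3 sets the population for its summary table: "The following non-drug therapies will be summarized by randomized treatment group and total and by indication for mITT participants". The items include NSx with craniotomy and DC, delayed intubation, and "Number (%) of participants with decision of CMO, time and reasons of CMO". The only output in that section on a wider set is a listing: "A listing of non-drug therapies for randomized participants will be provided".

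SAP 5.4 follows the same pattern. The summary reads "Number (%) of participants with any major protocol deviations will be summarized by randomized treatment group for mITT participants", and the wider output is again a listing: "A listing of major and minor protocol deviations for all randomized participants will be provided".

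SAP 3.6.1 defines mITT. Participants must be randomized and must receive study drug. The third condition concerns imaging: "have at least one final read per central review of contusion volume from an NCCT or MRI scan acquired between 10 hours after the initiation". The 10 hours run from the start of infusion. The scan window closes as follows: "and the Hour 96 visit or NSx or CMO (if earlier"). Protocol 16.2.1 defines the same population with a lower bound of 12 hours, and its window is closed by DC, IPH evacuation or CMO rather than by any NSx.

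**The concern.** The event being counted can be what removes the participant from the count. If NSx or CMO happens before Hour 10, the scan window in SAP 3.6.1 closes before it opens, so no scan can qualify. That participant is outside mITT and so outside the table of NSx and CMO. For deviations, a participant never dosed, or with no readable post-dose scan, is not counted even where that failure is itself a major deviation.

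DC and CMO matter beyond description. They truncate the primary endpoint, which then uses the last scan before the procedure. A reader judging whether truncation was balanced between arms will look for the DC and CMO rates by arm. As planned, those rates are conditioned on membership of a set that is fixed after randomization and depends partly on early deterioration, which treatment may affect.

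**Working it through.** **The plan's own figure.** The only sample-size figure is about 90% power for 15 mL, SD 29 mL, 80 per group (Protocol 16.8, SAP 2.3). The noncentrality is 15 / (29 × √(2/80)) = 3.27, and a two-sided 5% t-test on 158 df then has power 0.902. It reproduces, but nothing below depends on it. This is a check of analysis sets.

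**Which set each output uses.**

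| Output | SAP section | Set |
|---|---|---|
| NSx/DC, CMO: number (%) | 5.5.3 | mITT |
| Non-drug therapies: listing | 5.5.3 | randomized |
| Major deviations: number (%) | 5.4 | mITT |
| Deviations: listing | 5.4 | all randomized |
| End-of-treatment status | 5.2 | all randomized |
| Deaths | 5.7.3 | all randomized |
| Baseline characteristics | 5.3 | mITT and all randomized |
| Exposure | 5.5.1 | safety set |

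No visible section tabulates NSx/DC, CMO or major deviations on a wider set. SAP 5.5.3 also gives a dating rule for participants who never receive study drug. They cannot be in mITT, so within that section the rule can affect only the listing.

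**Who is outside mITT under SAP 3.6.1.**
- NSx or CMO before Hour 10: certainly outside.
- DC, IPH evacuation or CMO from Hour 10 to Hour 22: possibly outside. Protocol Table 2, footnote 5, accepts a scan up to 12 hours before these procedures. If that scan predates Hour 10 and there is no other, no read qualifies (10 + 12 = 22).
- Other NSx: the same footnote expects no scan, so membership depends on the scheduled scans.
- Never dosed, or no qualifying central read: outside.

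**Size.** The documents give no rate or timing for these events and no expected mITT loss. The figures below rest on assumed values and show only how the result moves.

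The share of events within 96 h that fall before Hour 10 is 10/96 = 10.4% if timing is uniform. If timing is exponential with median m, truncated at 96 h, it is (1 − 2^(−10/m)) / (1 − 2^(−96/m)): 17.9% for m = 48 h, 26.8% for 24 h, 44.0% for 12 h and 68.5% for 6 h.

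Suppose 10% of 160 (16) have such an event and only the early cases leave mITT. With share s lost, the table shows (16 − 16s) / (160 − 16s). For s = 0.104 this is 14.3/158.3 = 9.1%; for s = 0.69 it is 5.0/149.0 = 3.3%.

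These shares refer to events within 96 h. Protocol 11.4.2 records procedures through Day 180, and SAP 5.5.3 states no upper limit, so later events shrink the omitted share. If half the tabulated events came after Hour 96, 10.4% would become 5.2%.

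**Effect on the comparison between arms.** Take two arms of 80 with 16 events each (20% in both), all within 96 h, with assumed median timing of 48 h in one and 12 h in the other. The first loses 16 × 0.179 = 2.9 and shows 13.1/77.1 = 17.0%. The second loses 16 × 0.440 = 7.0 and shows 9.0/73.0 = 12.3%. Equal rates print as unequal because timing differs. The medians are invented; only the mechanism comes from the SAP.

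**Deviations.** With an assumed 48 of 160 (30.0%) having a major deviation and 24 outside mITT, the table shows 24/136 = 17.6% if all 24 had one, and 48/136 = 35.3% if none did. The count cannot rise, but the percentage can move either way.

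**The case against.** The main comparison is made in mITT, so describing intercurrent events and deviations in that set is coherent, and no test or decision rule uses these tables. That stands, and it is why the mITT tables should be kept.

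Foreseeable early events are largely screened out. Exclusion criterion 1 removes patients likely to have care withdrawn within 24 hours, criterion 2 those with an indication for immediate IPH evacuation or DC, and criterion 30 those likely to move to CMO at 24 to 96 hours. The Hour 24 scan, with the pre-procedure scan requested before DC, IPH evacuation or CMO, should keep most later cases in mITT. This also stands, with one limit: criterion 2 does not cover other neurosurgery, whereas SAP 3.6.1 closes the window at any NSx.

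The information is not lost. Both sections list all randomized participants, deaths and treatment discontinuation are summarized for all randomized participants, and adverse events for the safety set. A marked imbalance in early deterioration would probably show there. But a listing gives no rate by arm, and those other tables do not count DC or CMO.

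Protocol 16.2.1 can be read as admitting a pre-procedure scan taken before 12 hours, which would bring some early DC and CMO cases back into mITT. The SAP text does not allow that reading, and Protocol section 16 leaves the final details to the SAP.

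A reader might infer that many of these participants drop out of the tables. The documents give no figure to support that, and the points above argue for a limited number.

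**Conclusion.** The point holds as a defect in the reporting plan. SAP 5.4 and 5.5.3 tabulate major deviations, NSx/DC and CMO only in mITT, and SAP 3.6.1 by definition leaves out participants with NSx or CMO before Hour 10, undosed participants and those without a qualifying central read. Counts by arm of events that truncate the primary endpoint are therefore conditioned on a post-randomization event that treatment may affect. This rests on the SAP wording alone, not on an assumed rate.

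The size is unknown and probably limited. Three stronger readings are not supported. One is that about 10% of all DC and CMO cases go untabulated: that figure needs uniform timing and ignores procedures recorded after Hour 96. Another is that the printed deviation rate would be well below the true one: that requires every excluded participant to have had a major deviation, whereas late dosing, ineligible baseline values and early stopping can all occur in participants who remain in mITT. The third is that the primary efficacy result is thereby shown to be biased: the point concerns the conduct and intercurrent-event tables only.

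**What to change.** In SAP 5.4 and SAP 5.5.3, add summaries by randomized arm of major protocol deviations, NSx/DC and CMO for all randomized participants. Keep the mITT versions as companion tables, since they describe the set used for the main analysis. In SAP 5.2, add the number excluded from mITT by arm with reasons: not dosed, NSx or CMO before a qualifying scan, no scan, or no usable central read.

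So that the exclusions can be classified consistently, align the mITT wording: SAP 3.6.1 has 10 hours and any NSx, while Protocol 16.2.1 and SAP 5.6.2 have 12 hours and DC, IPH evacuation or CMO.

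The cost is a few extra tables. SAP 5.4 and 5.5.3 already list these data for randomized participants, so no new collection is needed and no efficacy analysis changes.
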